## 10.0 Vulnerable Populations

No involvement of special vulnerable populations, such as fetuses, neonates, pregnant women, children, prisoners, institutionalized individuals or others who may be considered vulnerable, will be included in this research.

## 11.0 Local Number of Subjects

Based on the PI's experience conducting exercise intervention studies, we conservatively estimate a 30% rate of attrition. Thus, in order to ensure we hit our target of  $N = 20$  intervention completers, recruitment will continue until  $N = 30$  participants provide informed consent to participate in the intervention portion of the study (see Consent Form Part 2).

## 12.0 Recruitment Methods

The research team has established a successful process by which study team members collaborate with DH clinicians to identify eligible patients each week. The PI ([name]) will apply for a Health Insurance Portability and Accountability Act (HIPAA) waiver to allow members of the study team to screen clinic schedules to identify potential study participants. Medical oncology members of the research team may also independently identify potential participants for the study team to contact. The PI and/or a study coordinator will consult with clinicians to confirm eligibility based upon clinical characteristics. If a patient appears to be eligible per initial review of stage and treatment regimen, a study coordinator will ask the provider to mention the study/provide a recruitment flyer/letter from the patient's care team

and obtain permission for the study team to contact her in clinic, by phone, or by postal mail in order to explain the study, determine eligibility, and initiate informed consent procedures.

**Strategies to minimize bias in sampling:** Eligibility criteria will be clearly defined so that the sample is not biased by relying on clinicians' determinations of a given patient's "appropriateness" or need for the study. Remote delivery of all study intervention and data collection procedures along with flexible staffing (i.e., the PI and/or Research Assistant available during early evening hours) will help address barriers to participation that may be experienced by participants who do not live locally and/or individuals with clinic appointments outside of regular business hours.

**Procedures to monitor enrollment and track and retain participants:** The Research Assistant will prepare weekly enrollment reports that will be reviewed at weekly meetings with the PI. The reports will summarize the number of individuals identified, screened, and enrolled. The Research Assistant will work with the recruiters to elicit and summarize any patient feedback and bring it to the PI to discuss with the research team and determine if adjustments to recruitment procedures or materials are warranted. Should attrition rates be higher than expected, the research team will strategize alternative retention strategies (e.g., higher participant compensation incentives, reduced assessment burden).

**Participant Incentives:** Participant payments will be provided at a rate of \$20 for completing each of the REDCap surveys (i.e., T1 REDCap survey and T2 REDCap survey). Additionally, participants will be compensated \$1 for each of the morning report and random EMA prompts completed during the 10-day assessment periods at baseline, 2-, 6-, and 12-weeks follow-up; thus, a total of \$120 can be earned for completing EMA assessments (\$1 X 3 EMA prompts/day X 10 days X 4 data collection periods). (Note, participants will not be paid for completing the during exercise EMAs reports to avoid encouraging over-reporting of exercise). Each participant, can earn a total of \$160\* for completing all study assessments.

At the Tele- Visit 1 appointment, participants will also be given a Fitbit activity tracker (to keep) as compensation for their participation and to encourage behavioral self-monitoring as part of the core exercise intervention. If participants decide to terminate their participation in the study early (before the week 12 follow-up assessment), we will ask that they return the Fitbit monitor given to them at the Tele- Visit 1 appointment. In this case, we would provide them a pre-paid envelope and ask they follow instructions to mail the Fitbit back at their earliest convenience. This will be explained to participants during the consent process.

## 13.0 Withdrawal of Subjects

Participants will be withdrawn from the study at their request. The research team will continue attempts to contact participants for each session and study assessment unless and until they ask us to stop/express the desire to withdraw. Each study contact is an extension of informed consent where participants are told what is occurring, what happens next, and that their participation is voluntary. When we are unable to reach participants by telephone for at least 14 days we send a letter conveying our attempts to reach them and ask them to contact us to continue with study activities or withdraw, as they prefer. Participants may be withdrawn from the research without their consent if they experience any medical events (after enrollment) that would make it unsafe for them to continue participation in an unsupervised exercise intervention (e.g., myocardial infarction).

## 14.0 Risks to Subjects

The study intervention procedures and assessments are not invasive and do not involve pharmacological agents, thus, we anticipate that there will be a low risk of adverse events associated with participation in the proposed research. Potential risks involved with participation include:

- i. Breach of Confidentiality
- ii. Exercise-Related Injury or Discomfort
- iii. Risk of Distress

**Breach of Confidentiality:** To address potential loss of confidentiality, study ID numbers will be used on all study documents, in place of personally identifying information, and all electronic data will be saved on a server protected by the Dartmouth Cancer Center's firewall.

**Exercise-Related Injury or Discomfort:** Regarding risks related to exercise, the study Control intervention (intensity-regulated exercise prescription) reflects the current standard for prescribing exercise during cancer survivorship and the experimental Affect-Rx intervention (affect-regulated exercise prescription) *explicitly instructs participants to avoid experiences of discomfort/displeasure during exercise.*

Participants will be provided their assigned exercise prescription and encouraged to increase their weekly activity levels to be commensurate with recommended guidelines, but the study will not expose participants to in-person exercise sessions or classes, and participants will not be required to use any exercise-related equipment. Therefore, the study does not expose participants to additional risks related to exercise. However, there is always some inherent risk of injury when engaging in exercise (e.g., a participant could fall while walking). To manage this risk, participants will be informed of both the risks and benefits of exercise. Further, study inclusion criteria (i.e., medical clearance for exercise) are designed to identify and exclude patients for whom exercise will be unsafe.

**Risk of Distress:** It is not anticipated that participants are likely to experience distress in response to the nature of the assessments collected for this research; however, it is conceivable that completing some survey measures or reflecting on one's behavioral patterns could elicit distress or cause participants to feel uncomfortable. The PI is a licensed clinical psychologist and is trained to validate feelings of frustration and distress while re-directing participants to actionable ways of making immediate progress. Likewise, the Research Assistant will be trained to listen for signals of distress (e.g., long pauses, crying) and respond tactfully (e.g., do not indicate verbally or non-verbally that they are uncomfortable with participant distress) and to remind the participants participation is voluntary and assessments can be paused or returned to a later time if needed.

## 15.0 Potential Benefits to Subjects

Participants will not be promised benefits as a result of their participation in the proposed research. However, all participants will receive a core exercise intervention designed to promote exercise engagement consistent with recommended guidelines. Thus, all participants may benefit by learning about recommended guidelines for exercise during cancer survivorship and meeting with the study team to discuss goals and plans for increasing their exercise behavior. Participants may also notice a reduction in cancer-related adverse effects (e.g., fatigue) or improvements in physical functioning and/or health-related quality of life as a result of increasing their exercise behavior. The risks of the study are minimal to individuals in relation to the potential benefits they may receive from increased exercise participation.

## 16.0 Statistical Analysis Plan

**Analysis Plan & Power Analysis:** There are no definitive guidelines for determining the size of a pilot study in healthcare research, and, according to guidelines provided by ORBIT, for this early phase of intervention development, "*The sample size can be small because clinical, not statistical, benefit is sought and sample size calculations are unnecessary*" (pg. 977). Nevertheless, our target sample size of

*N* = 20 intervention completers is consistent with typical sample size targets used in similar early-phase open pilot studies.

**Aim 1 (ORBIT Phase Ib).** To modify and refine the Affect-Rx exercise prescription and study protocol to be acceptable for use with breast cancer survivors. Modifications and refinements will be informed by semi-structured participant interviews and objective indicators of acceptability assessed using the Treatment Acceptability and Preferences (TAP) Measure, accelerometer wear-time, and daily EMA survey completion.

**Analysis of Aim 1 Quantitative Data:** Responses to the Treatment Acceptability and Preferences TAP Measure will be scored, distributions will be examined, and data will be assessed for completeness. Rates of accelerometer wear-time compliance and daily ecological momentary assessment (EMA) completion will similarly be examined for completeness and described as percentages and proportions.

**Analysis of Aim 1 Qualitative Data:** Qualitative data will be transcribed and analyzed in accordance with guidelines specified by NIH-Best Practices for Qualitative Research in the Health Sciences for applicability, preferences, clinical relevance, intervention length/timing, and challenges. Coding and categorizing the data will be followed by comparing and contrasting categories to identify overarching themes and similarities and dissimilarities among patients' experiences and perspectives. The evolving analysis will be tracked using memos and shared during regular study team meetings to enhance rigor and develop the findings and interpretations.

**Analysis Plan for Exploratory Outcomes:** Patient reported outcome measures collected on the T1 and T2 REDCap surveys will be scored and distributions will be examined and assessed for completeness. Pre/post intervention change on these measures will be evaluated using t-tests and ANCOVA tests, when appropriate, to control for covariates. These analyses are for exploratory purposes to inform effect size estimates for a future fully-powered efficacy trial.

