## 5.0 Procedures Involved

**Study Design Overview:** Physically inactive breast cancer survivors be recruited to participate in a pilot study promoting adherence to recommended weekly physical activity guidelines for breast cancer survivors. All participants will receive a core exercise promotion intervention and their daily activity levels and feeling states (affect) will be measured using EMA and accelerometry over a 12-week period with measurement burst assessment at baseline and 2-, 6-, and 12-weeks follow-up.

**Study 1.**  $N = 30$  participants will receive the core exercise promotion intervention plus an affect-regulated exercise prescription (Affect-Rx) in this single-arm pilot. The ORBIT model recommends patient stakeholders be involved in the development of interventions intended to serve them as early as possible in the translational process, thus, this study will be used to modify and refine the intervention protocol and study assessment schedule to be acceptable to the target population of physically inactive, stage 0-III breast cancer survivors.

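### Pre/post effect sizes meant to inform a future efficacy trial will rest only on participants with both surveys, although up to 30% attrition is expected and no sensitivity range is planned

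*Combined protocol and SAP*

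**What the plan says.** Section 16.0, in the plan for exploratory outcomes, says of the survey measures: "Pre/post intervention change on these measures will be evaluated using t-tests and ANCOVA tests, when appropriate, to control for covariates". It then gives the purpose: "These analyses are for exploratory purposes to inform effect size estimates for a future fully-powered efficacy trial". On missing data it says only that the measures "will be scored and distributions will be examined and assessed for completeness". It names no analysis set, missing-data method or sensitivity analysis.

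Section 11.0 says "we conservatively estimate a 30% rate of attrition". Recruitment therefore continues until 30 "participants provide informed consent to participate in the intervention portion of the study", to reach a target of 20 completers. Section 16.0 defends that target by precedent: "20 intervention completers is consistent with typical sample size targets used in similar early-phase open pilot studies".

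Under section 5.0, T1 is completed after consent and before Tele-Visit 1, and T2 is sent by emailed link at the end of the 12 weeks. On people who stop engaging, section 13.0 says: "The research team will continue attempts to contact participants for each session and study assessment", until they ask to withdraw. The study has no comparator; section 5.0 describes the participants as treated "in this single-arm pilot".

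**The concern.** The effect size is the declared product of this analysis, so the people it describes matter. A t-test of within-person change, or an ANCOVA with T2 as the response, drops anyone without a T2 score. The plan does not choose this; it follows from the tests named. If 30% of T2 surveys are missing, the estimate describes about 21 of 30 people, and the T1 data of the other 9 go unused.

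The protocol's own reasoning makes it plausible that those lost did less well. Section 2.0 links pleasant exercise to adherence, and section 15.0 expects any benefit in fatigue, function or quality of life to come from exercising more. If so, the change among those retained overstates the change among all who started. A later trial that took the figure over unadjusted, and aimed at the effect in everyone enrolled, would be too small.

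**Working it through.** **Inputs from the documents.** Attrition 30% and recruitment 30 (section 11.0); target completers 20 (sections 11.0 and 16.0); t-tests and ANCOVA on T1 and T2 (section 16.0).

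**The plan's own figure.** 20 / (1 − 0.30) = 28.6, rounded up to 29, against the stated 30. In reverse, 30 × 0.70 = 21 with T2 and 9 without. The recruitment target reproduces.

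**Assumptions.** The documents give no effect size, SD, alpha, power or design for the future trial. For illustration I take a standardised effect of d = 0.50 in those with T2, two arms 1:1, two-sided 5%, 80% power, normal approximation. I also take it that all the attrition appears as missing T2. Let r be the mean change of those without T2 as a fraction of the mean change of those with T2. The documents give no value for r.

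**Formulas.**
- Effect in all enrolled = d × (0.70 + 0.30r), SD held constant.
- Inflation of the carried-forward effect = 1 / (0.70 + 0.30r).
- Number per arm = 2 × (1.96 + 0.84)² / effect², rounded up. For d = 0.50 this gives 63 per arm.

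| r | Effect in all enrolled | Inflation | Needed per arm | Planned / needed |
|---|---|---|---|---|
| 0 | 0.350 | 1.43 | 129 | 0.49 |
| 0.25 | 0.3875 | 1.29 | 105 | 0.60 |
| 0.5 | 0.425 | 1.18 | 87 | 0.72 |
| 0.75 | 0.4625 | 1.08 | 74 | 0.85 |
| 1 | 0.500 | 1.00 | 63 | 1.00 |

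At r = 0, 63 per arm has about 50% power. The ratios are nearly the same for d from 0.3 to 0.8. An exact t-based calculation adds about one per arm (64 and 130 at r = 1 and r = 0).

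**Dependence on the SD.** At r = 0, mixing two groups with different mean changes gives variance 1 + 0.7 × 0.3 × 0.50² = 1.0525, so 135 per arm and a ratio of 0.47. If instead each dropout is assigned exactly zero change, the variance falls to 0.7 + 0.21 × 0.50² = 0.7525. Then 97 per arm are needed and the ratio is 0.65. The standardiser therefore has to be stated.

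**What a mixed model would do.** With two time points and dropout only at T2, the model's mean change equals the change in those with T2 plus (b − 1) × (T1 mean of all − T1 mean of those with T2), where b is the slope of T2 on T1 in those with T2. If the two groups have the same T1 mean, the second term is zero and the estimate does not move, however differently the dropouts changed.

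**Sampling error.** At n = 20, an observed standardised change of 0.50 has a 95% CI of about 0.03 to 0.96.

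**The case against.** The strongest reply is that this is an acceptability pilot. The analyses are labelled exploratory, nothing it concludes depends on them, and the later trial's size is not set here. All of that stands and limits the severity.

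The 30% is also a deliberately cautious planning figure for completers, not a forecast of missing T2 surveys. Someone may stop exercising and still return T2: contact continues until withdrawal, the survey is remote, and section 12.0 pays $20 for it. Against that, section 12.0 describes early termination as leaving before the week 12 assessment, so some attrition will mean a missing T2. The 30% is best read as an upper planning value.

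Loss will be partly visible already. Retention is reported against everyone enrolled (section 3.0), and withdrawals and sources of data loss are reviewed monthly (section 17.0). This shows how many were lost, but not what their loss does to the effect size.

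The direction of bias is not established. The outcomes are survey scores, and no passage says how people without T2 change on them. That also stands, and it is why a range is needed rather than a correction.

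Finally, a single-arm change is not a between-group effect even with complete data, and the interval at n = 20 is wide. The per-arm figures above therefore show proportions, not a forecast of any trial's size.

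**Conclusion.** The point holds as a minor one. The named tests use only participants with both surveys, the plan allows for up to 30% attrition, and the estimates are meant for use in planning a later trial with nothing to show how they depend on those lost.

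If people without T2 changed less, the carried-forward effect is 1.0 to 1.43 times the effect in all enrolled, and the planned size is about 49%, 72% or 100% of the needed number at r = 0, 0.5 or 1. This assumes 30% missing T2, a constant SD and unadjusted use of the estimate. Values of r outside 0 to 1 cannot be excluded from the documents; above 1, the bias would reverse.

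A reader might infer more than this:
- That the plan prescribes a completers-only analysis. It does not say so; this is the default result of the tests.
- That the next trial would be planned at about half its needed size. That is the zero-change, constant-SD case. The documents give no value for the dropouts' change and no rule for turning the pilot estimate into a sample size.
- That a mixed model would remove the bias. It assumes data missing at random and cannot correct for dropout related to the unobserved change.

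**What to change.** In section 16.0, under the exploratory outcomes:

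1. Define the analysis set as everyone who consents to the intervention portion and has a T1 score. Estimate mean change with a model of T1 and T2 that keeps all of them, and report it with a 95% CI.
2. Compare T1 scores between participants with and without T2.
3. Beside every effect size carried forward, report a sensitivity range in which those without T2 change by 0% to 100% of the mean change in those with T2, using the observed proportion missing. State the SD used as the standardiser.
4. State that the model assumes missing at random, so the range in item 3 is what addresses dropout related to unobserved change, and that these are single-arm changes and not between-group effects.

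The cost is a few sentences and a little more analysis, with no new visits, data or participants. The downside is that the reported effect size will come with a wider range and may be smaller.

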## 17.0 Provisions to Monitor the Data to Ensure the Safety of Subjects

**Overall Framework for Data and Safety Monitoring and Information to Be Monitored:** All study data will be kept confidential during all study phases. A password-protected dataset will cross-reference study ID numbers and study data. The HIPAA-compliant Citrix Sharefile cloud-based platform will serve as backup and storage of files and data. The Dartmouth-Hitchcock electronic medical record system (EPIC) and REDCap platform are backed up daily. Integrity and privacy of data entered into an electronic database will be achieved using industry-standard encryption and a granular security permission scheme down to information at the individual level. Data safety will be ensured by redundant server hardware deployment and database backups. Several levels of password protection will be implemented and passwords will be changed regularly. Transcripts from exit interviews will be digitally recorded and transcribed. Any data-related paper records will be kept in a locked filing cabinet. In order to ensure fidelity to the study protocol and integrity of data, the following procedures will be implemented: a) frequent meetings between the PI and Co-Investigators to troubleshoot recruitment and data collection issues, b) use of data entry software (i.e., REDCap) that provides entry validation range tests and is designed to minimize missing data by flagging missed items before surveys are submitted, c) weekly monitoring of the completeness of data collected from the LifeData mobile app, d) accelerometer data download and back up upon return by mail.

This research involves no more than minimal risk to participants. Nevertheless, we have carefully thought through our procedures for monitoring the data to ensure the safety of participants. In order to ensure participant safety, data integrity, and validity, the PI ([name]) will be responsible for reviewing the following information on a monthly basis: number of participants completing the protocol; subject

withdrawal and sources of data loss; any serious or minor adverse consequences and actions taken to remedy the issue; new, timely information that could impact efficacy and/or safety of the program or procedures. The PI will assure that informed consent is obtained prior to performing any research procedures, that all participants meet eligibility criteria, and that the study is conducted according to the IRB-approved research protocol.

**Reporting of Adverse Events:** All members of the study team will be trained to report all adverse events. In addition, screening for adverse events potentially related to the study procedures will occur during the routine administration of study assessment measures. The course of each adverse event will be followed until resolution, stabilization, or until it has been determined that the study treatment or participation is not the cause. The PI will conform to the adverse event reporting timelines, formats and requirements of the various entities to which they are responsible, but at a minimum, events that will be reported are those that are:

- related to study participation,
- unexpected, and
- serious or involve risks to subjects or others

**Significant Adverse Events:** If a significant adverse event occurs, the PI will report the event to the Cancer Center's CCRC and Dartmouth-Hitchcock IRB using the online reporting system and the team will follow institutional protocols with respect to reporting within 14 days of the PI's knowledge of the significant adverse event. The PI, in consultation with study co-investigators, will review the adverse event report and gather other information as needed to investigate the event and determine the need for subsequent action. Any subsequent action will be documented and reported to the IRB. The IRB will review each reported adverse event to determine whether: the participants in the study should receive additional information related to continuing their participation; the protocol, study plan or consent form should be modified; or the study should be temporarily suspended. If the IRB determines that some action in response to the adverse event is necessary, the IRB will promptly inform the PI. All deaths will be reported in an expedited manner within 24 hours of the PI's knowledge. The report of death will be submitted to the NIH Program Officer, Dartmouth-Hitchcock IRB, and DSMAC Chair.

**Post-study adverse event:** All unresolved adverse events will be followed by the PI until the events are resolved, the participant is lost to follow-up, or the adverse event is otherwise explained. At the last scheduled visit, the PI will instruct each participant to report any subsequent event(s) that the participant, or the participant's personal physician, believes might reasonably be related to participation in this study. Serious adverse events that are still ongoing at the end of the study period will be followed up to determine the final outcome. Any serious adverse event that occurs after the study period and is considered to be possibly related to the study intervention or study participation will be recorded and reported immediately.

**Stopping Rules:** Significant risk is not anticipated in this study due to the supportive and non- invasive nature of the intervention. However, the PI will summarize adverse event data annually to the DSMAC for consideration of study continuation. Interim analyses will only be conducted as requested by the DSMAC. The trial will be stopped only should there be IRB-related issues pertaining to unexpected safety risks.

